12.1.12. Laboratory Assessments

All laboratory assessments are to be tested either locally or centrally as indicated in the Table of Events, [Section 7, Table 3](#). Screening laboratory values must demonstrate subject eligibility; screening laboratory values may be repeated within the screening window if necessary.

12.1.12.1. Real-Time Reverse-Transcriptase-Polymerase-Chain-Reaction (rRT-PCR)

For initial diagnostic and follow-up testing for COVID-19, there are varied specimen options for analysis. The CDC recommends collecting and testing upper respiratory (nasopharyngeal and oropharyngeal (if possible) swabs), and lower respiratory (sputum, if possible) for those subjects with productive coughs. Induced sputum may be collected if institutional practice allows. Testing may also be performed on blood (serum) samples. Institutional practices for the collection procedures and appropriate precautionary practices for avoiding transmission must be followed at all times.

For intubated subjects, endotracheal aspirate should be collected as outlined in the Table of Events.

Refrigerate specimen at 2-8°C until testing can be performed. Samples for screening should be prioritized on for testing as the results are required in order to intervene in a timely manner.

Note: Baseline testing for the detection of SARS-CoV-2 to confirm eligibility should be performed using rRT-PCR or other approved test based on institutional practice. All subsequent testing for the detection of SARS-CoV-2 should be performed by rRT-PCR.

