6.9. Efficacy Endpoint Definitions

- **Time to Clinical Improvement by OSCI**: defined as the time from the date of randomization to the first date of clinical improvement measured by OSCI. (Appendix D). Clinical improvement is defined as an improvement at least by cross category (or Patient State improvement in Appendix D table, such as from Hospitalized Severe Disease to Hospitalized Mild Disease). Subjects who do not have clinical improvement on or before Study Day 28 will be censored at Study Day 28.
- **Clinical Status by OSCI**: defined by the Ordinal Scale score of 0 to 8 by OSCI (Appendix D).
- **Rate of Clinical Improvement by OSCI**: defined as the proportion of subjects who achieved clinical improvement by OSCI.
- **Time to Clearance of SARS-CoV-2**: defined as the time from the date of randomization to the clearance of SARS-CoV-2 by rRT-PCR by two negative results at least 24 hours apart, with the first negative as the start date of clearance. Specimens included are nasopharyngeal swab and oropharyngeal swab (if available). Subjects who do not have clearance on or before Day 28 will be censored at Day 28.
- **Rate of Clearance of SARS-CoV-2**: defined as the proportion of subjects with “negative” measurement of COVID-19 by rRT-PCR.
- **Time to Clinical Improvement by NEWS2**: defined as the time from the date of randomization to the first date of clinical improvement. Clinical improvement is defined as improvement of clinical symptoms as measured by the NEWS2 Score (Appendix C). Subjects who do not have clinical improvement on or before Study Day 28 will be censored at Study Day 28.
- **Rate of Clinical Improvement by NEWS2**: defined as the proportion of subjects who achieved clinical improvement.
- **Time to Pulmonary Clearance**: defined as the time of randomization to the date of pulmonary clearance. This is defined as disappearance of virus from LRT- specimen where it has previously been found (induced sputum if available, endotracheal aspirate if available). Subjects who do not have pulmonary clearance on or before Study Day 28 will be censored at Study Day 28.
- **Pulmonary Clearance Rate**: defined as the proportion of subjects who achieve pulmonary clearance.

- **Duration of Hospitalization:** defined as date of randomization to the date of medical discharge. Subjects who are not discharged on or before Study Day 28 will be censored at Study Day 28.

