7. TABLE OF EVENTS

[figure not shown]
Table 3: Table of Events

Event	Screen	Treatment Period						Follow-up period ^w			
	Baseline ^a	Day 1 ^k	Day 4 (+ 2 days) ^k	Day 7 (+ 2 days) ^k	Day 15 (± 2 days)	Day 21 (± 2 days)	Day 28 (± 2 days)	Day 90 (±14 days)	Day 180 (±14 days)	Hospital Discharge ^v (if applicable)	Early Termination ^b
Study Entry and General Assessments											
Study Informed Consent	X	-	-	-	-	-	-	-	-	-	-
Inclusion/Exclusion Assessment	X	-	-	-	-	-	-	-	-	-	-
Pre-ICF rRT-PCR (or other approved test per institutional practice) results confirming SARS-CoV-2	X	-	-	-	-	-	-	-	-	-	-
Demographics/Medical history	X	-	-	-	-	-	-	-	-	-	-
Treatment and Study Required concomitant medications											
Phase II only: Randomization to CYNK-001 or Best Supportive Care (1:1 ratio) after treatment eligibility is confirmed	X	-	-	-	-	-	-	-	-	-	-
CYNK-001 IV infusion ^{c,d}	-	X	X	X ^e	-	-	-	-	-	-	-
Best supportive care - Control group (Phase II only)	-	Control group to receive Best Supportive Care only						-	-	-	-
Acetaminophen 650mg PO pre- and post-medication ^d	-	X ^{f,k}	X ^{f,k}	X ^{f,k}	-	-	-	-	-	-	-

CYNK-001
Celularity Inc

[figure not shown]
CYNK-001-COVID-19

[figure not shown]

[figure not shown]

[figure not shown]
CYNK-001
Celularity Inc

CYNK-001-COVID-19

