8. SELECTION AND WITHDRAWAL OF SUBJECTS

8.1. Subject Inclusion Criteria

1. Subject has confirmed positivity for SARS-CoV-2 as measured by rRT-PCR or other approved test to detect SARS-CoV-2 per institutional practice.
2. Subject is experiencing any symptom/clinical sign of COVID-19 illness or has a positive disease-related chest x-ray/CT scan at screening.
3. Subject is ≥ 18 years of age at the time of signing the Study informed consent form (ICF).
4. Subject understands and voluntarily signs the Study ICF prior to any study-related assessments/procedures are conducted.
5. Subject is willing and able to adhere to the study schedule and other protocol requirements.
6. $\text{SpO}_2 \geq 88\%$ on room air; oxygen is permitted as delivered by nasal cannula and/or face mask at any flow rate to achieve this SpO_2 . Subjects must have an $\text{SpO}_2 \geq 92\%$ if on supplementary oxygen.
 - *(Note: Once eligibility is confirmed, to initiate CYNK-001 treatment, an increase of supplemental oxygen of greater than or equal to 50% from baseline/screening resulting in oxygen use of greater than 8L -or- a change in mode of supplemental oxygen delivery with the intention to deliver oxygen more frequently requires consultation with the medical monitor)*
7. Ability to be off immunosuppressive drugs for 3 days prior to infusion, unless clinically indicated. Steroids are permitted if clinically indicated and at the discretion of the treating physician. If clinically indicated, careful consideration should be taken regarding the timing and tapering of high-dose steroids.
8. Female of childbearing potential (FCBP)* must not be pregnant and agree to not becoming pregnant for at least 28 days following the last infusion of CYNK-001. FCBP must agree to use an adequate method of contraception during the treatment period.
 - a. *FCBP is a female who: 1) has achieved menarche at some point, 2) has not undergone a hysterectomy or bilateral oophorectomy or 3) has not been naturally postmenopausal (amenorrhea following cancer therapy does not rule out childbearing potential) for at least 24 consecutive months (i.e., has had menses at any time in the preceding 24 consecutive months).
9. Male subjects must agree to use a condom during sexual contact for at least 28 days following the last infusion of CYNK-001, even if he has undergone a successful vasectomy.

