13.2 Efficacy Endpoints

The study includes the following efficacy endpoints:

- 1) Clinical status by OSCI at Day 28.
- 2) Clinical improvement by OSCI by Day 15.
- 3) Rate of clinical improvement by OSCI at Day 28. The rate is defined as the proportion of subjects who achieved clinical improvement by OSCI on or prior to Day 28.
- 4) Time to clinical improvement as measured by OSCI.
- 5) Time to clinical improvement by NEWS2. Time to clinical improvement by NEWS2 is defined as the time from the date of randomization (date of first dose of CYNK-001 for Phase 1) to the first date of clinical improvement by NEWS2. Clinical improvement by NEWS2 is defined as a 25% decrease compared to baseline in the NEWS2 Score. Subjects without clinical improvement by NEWS2 on or before Day 28 will be censored at Day 28.

- 6) Rate of clinical improvement by NEWS2 at Day 28. The rate is defined as the proportion of subjects who achieved clinical symptom improvement by NEWS2 Score on or prior to Day 28.
- 7) Rate of clearance of SARS-CoV-2 from mucosal specimens at Day 28. Rate is defined as the proportion of subjects with clearance of SARS-CoV-2 by rRT-PCR by two negative results at least 24 hours apart. Specimens included are nasopharyngeal swab and optional oropharyngeal swab.
- 8) Time to clearance of SARS-CoV-2 from mucosal specimens at Day 28. Clearance is defined as the time from the date of randomization to clearance of SARS-CoV-2 by rRT-PCR by two negative results at least 24 hours apart. Specimens included are nasopharyngeal swab and optional oropharyngeal swab.
- 9) Time to pulmonary clearance at Day 28. Clearance is defined as the time from randomization to the date of pulmonary clearance. This is defined as disappearance of virus from LRT specimen where it has previously been found (induced sputum and endotracheal aspirate if available).
- 10) Rate of pulmonary clearance at Day 28. Rate is defined as the proportion of subjects who had disappearance of virus from LRT specimens where it has previously been found.
- 11) Duration of hospitalization from date of hospitalization to date of medical discharge.
- 12) For subjects requiring supplemental oxygen, the days with supplemental oxygen-free up to Day 28.
- 13) Proportion of subjects who need invasive or non-invasive ventilation up to Day 28.
- 14) SOFA score for subjects admitted to the ICU from ICU admission to ICU discharge, up to Day 28.

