14.7 Infectious Symptom Assessment

The infectious symptom assessment will be tabulated over time with the proportion of clinical status assessment as defined in the CRF. The descriptive statistics, including the proportion and its 95% confidence interval will be provided.

No missing data will be imputed for this part of analysis nor formal hypothesis testing will be performed.

Subject level listing of AEs, vital signs, laboratory assessments and inflammation assessments will be provided.

15. Changes in Conduct or Planned Analyses from the Protocol

Description of change of conduct: Early termination of the study by the company.

In review of the current status and enrolment challenges of the CYNK-001-COVID-19 clinical trial and given the current landscape of the COVID-19 pandemic and the rollout COVID-19 vaccine, a decision by

Celularity has been made to close the CYNK-001-COVID-19 clinical trial. As a result of this early termination, only 7 patients were enrolled and dosed in the Phase I portion.

Due to this change, a brief clinical study report will be provided instead of a full CSR. Based on this change, only the following analysis will be provided for Phase I along with supporting listings:

- Summary of Subject disposition
- Summary of major protocol deviations
- Summary of demographics and baseline characteristics
- Analysis of time to clinical improvement by NEWS2 score
- Analysis of rRT-PCR tests and time to clearance of SARS-CoV-2 by rRT-PCR results (if enough data available)
- Analysis of SOFA scores (if enough data available)
- Summaries of adverse events
- List of deaths
- Summaries of laboratory results, shift from baseline and abnormal laboratory values
- Summaries of vitals signs, oxygen saturation and ECG and shifts from baseline
- Summary of abnormal post-baseline QTc results

16. Analysis of Concomitant Medication and Concomitant Procedure

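### Mucosal SARS-CoV-2 clearance is not limited, in the visible text, to subjects who are rRT-PCR positive at baseline, so subjects already negative count as early clearances

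*Protocol*

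**What the plan says.** **Entry.** Inclusion criterion 1 (Protocol 8.1) reads: "Subject has confirmed positivity for SARS-CoV-2 as measured by rRT-PCR or other approved test to detect SARS-CoV-2 per institutional practice". The Table of Events (Protocol 7) lists the qualifying result as "Pre-ICF rRT-PCR (or other approved test per institutional practice) results confirming SARS-CoV-2", so it may predate consent. No maximum age for that result is visible.

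**Later testing.** Protocol 12.1.12.1 says that baseline testing to confirm eligibility "should be performed using rRT-PCR or other approved test based on institutional practice", then states: "All subsequent testing for the detection of SARS-CoV-2 should be performed by rRT-PCR".

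**Clearance.** Protocol 6.9 measures time to clearance from randomization and defines clearance "by two negative results at least 24 hours apart, with the first negative as the start date of clearance". The Protocol 6.9 rate is looser: it asks only for a negative rRT-PCR measurement. SAP 13.2, item 7, states: "Rate is defined as the proportion of subjects with clearance of SARS-CoV-2 by rRT-PCR by two negative results at least 24 hours apart". Item 8 uses the same two-negative rule for the time.

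**Analysis set.** SAP 13.3 analyses secondary endpoints in the ITT population unless otherwise specified, and SAP 7 defines that population as everyone randomized.

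**Contrast.** Pulmonary clearance, in the same two sections, counts disappearance of virus only from lower respiratory specimens in which it was found earlier.

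**After early closure.** SAP 15 keeps for Phase I: "Analysis of rRT-PCR tests and time to clearance of SARS-CoV-2 by rRT-PCR results (if enough data available").

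**The concern.** Clearance means a change from virus present to virus absent. The mucosal rule tests only the second half. A subject can reach the first study swab already rRT-PCR negative in two ways: by entering on a non-PCR test that rRT-PCR does not confirm, or by entering on an earlier positive rRT-PCR and clearing before Day 1. Either subject meets the definition at the first two swabs, with a time near zero.

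Such subjects say nothing about treatment. They raise the clearance rate, shorten the time to clearance and pull the arms together. In Phase I there is no control arm to show the same effect, so an already-negative subject would look like a rapid response to CYNK-001.

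**Working it through.** **1. Does the text close the gap?** The places where a baseline condition could sit, side by side:

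| Place | Prior positive rRT-PCR required? |
|---|---|
| Inclusion criterion 1 (Protocol 8.1) | No, another approved test is enough |
| Mucosal clearance, time and rate (Protocol 6.9) | No |
| Mucosal clearance (SAP 13.2, items 7 and 8) | No |
| ITT population (SAP 7) | No, all randomized |
| Per-protocol sensitivity analysis (SAP 13.4) | Not applicable; covers OSCI and NEWS2 only |
| Pulmonary clearance (Protocol 6.9; SAP 13.2, items 9 and 10) | Prior detection in the specimen is required |

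The condition was written for one virological endpoint and not for the other.

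**2. Inputs for an illustration.** The documents give no clearance times and no baseline-negative share. I borrow the OSCI planning medians (8 and 16 days, 36 per arm, 28 days; Protocol synopsis, SAP 6) and assume exponential times and baseline-negative shares f of 10, 20 and 30% in both arms, each such subject counted as cleared at Day 3.

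**3. The plan's own figure.** Under these assumptions the event probabilities by Day 28 are 1 − 2^(−28/8) = 0.912 and 1 − 2^(−28/16) = 0.703, giving 36 × (0.912 + 0.703) = 58.1 events. Freedman's formula gives Φ(√58.1/3 − 1.645) = 81.5%, which agrees with the stated power of at least 81% at one-sided 0.05. That figure concerns OSCI; it shows only that the model matches the sponsor's planning model. At two-sided 0.05, Schoenfeld's formula gives Φ(√58.1 × ln 2 / 2 − 1.96) = 75%.

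**4. Medians and rates as written.** After Day 3 the uncleared proportion is (1 − f) × 2^(−t/m), where m is the true median. Setting this to one half gives an observed median of m × [1 + log2(1 − f)]. The observed Day 28 rate is 1 − (1 − f) × 2^(−28/m), so the difference in rates shrinks by the factor (1 − f).

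| f | Control median (days) | Control rate | CYNK-001 rate | Difference (points) |
|---|---|---|---|---|
| 0 | 16.0 | 70% | 91% | 21 |
| 10% | 13.6 | 73% | 92% | 19 |
| 20% | 10.8 | 76% | 93% | 17 |
| 30% | 7.8 | 79% | 94% | 15 |

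**5. Power, two-sided log-rank, by simulation.** Ranges cover independent runs of 1,500 to 4,000 trials. With f = 0, power was 73 to 76%.

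| f | As written | Baseline positives only |
|---|---|---|
| 10% | 65–68% | 67–71% |
| 20% | 58–59% | 65–67% |
| 30% | 51–53% | 59–62% |

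The restriction recovers roughly 2 to 9 points within runs, or about 5 to 13 if clearance is dated close to Day 1. The rest of the fall comes from having fewer informative subjects, and no definition restores that.

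**6. A second illustration, on the rate.** Assume true clearance of 50% against 80% among baseline positives. Observed rates are f + (1 − f) × p. At f = 30% they are 65% and 86%, so the difference falls from 30 to 21 points. Approximate power (two-sided 0.05, 36 per arm) falls from 77% to 70/63/55% for f = 10/20/30% as written, against 73/67/61% when restricted.

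**The case against.** **Clearance implies prior positivity.** This is a natural reading, but the sponsor spelled out prior detection for pulmonary clearance and left it out here. A programmer following the mucosal rule would count the baseline negatives.

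**The missing text may settle it.** This stands in part. Most of the Table of Events is not shown, and some text after the Kaplan-Meier method in SAP 13.3 is redacted. A baseline swab may well be scheduled. The finding is therefore confined to the visible text.

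**The stakes are limited.** This stands. SAP 13.3 plans no formal hypothesis for secondary endpoints, describes their analysis as hypothesis generating and offers p-values for information only. Power is thus a weak measure of harm here.

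**Stronger readings that a reader might infer.** The documents do not support these:

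- *The arms are compared with bias.* Under 1:1 randomization, baseline negativity is balanced in expectation. The effect is dilution and loss of meaning.
- *The whole fall in power, from about 75% to 51–53% at a 30% share, is caused by the definition.* Most of it remains after the restriction.
- *One already-negative subject moves a Phase I clearance rate by 1/7, or 14 points.* SAP 15 names rRT-PCR tests and time to clearance, conditional on enough data, and does not name the rate. With 7 subjects and supporting listings, such a subject could also be seen directly. Phase I has no ITT population either. Its analyses use the safety set (SAP 4.8), which likewise carries no baseline rRT-PCR condition.

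**Conclusion.** The point holds for the visible text. Followed as written, the mucosal clearance rate and time include subjects with nothing to clear at the first study swab. The direction is clear: a higher rate, a shorter time and a smaller difference between arms. The size is not known, because it depends on a baseline-negative share that the documents do not give. The 8- and 16-day medians belong to OSCI, and the 10 to 30% shares and the Day 3 clearance date are assumptions. On those assumptions the control median could be halved at a 30% share, while the power that better wording can recover is modest. The case for changing the rule is chiefly that the estimate should mean clearance. The point is confined to secondary endpoints and to the Phase I time-to-clearance analysis retained after closure; the primary OSCI endpoint and pulmonary clearance are not affected.

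**What to change.** In SAP 13.2 and 13.3:

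- Base the main analysis of mucosal clearance rate and time on subjects with a positive rRT-PCR mucosal study swab taken on or before Day 1 and before any CYNK-001 infusion. If there is more than one such swab, use the latest; otherwise an old positive reopens the gap.
- Use the same swab window in both arms. SAP 12 defines Study Day 1 by the first CYNK-001 dose, so the control-arm equivalent must be stated.
- Report by arm the numbers who are baseline-negative and the numbers with no baseline rRT-PCR swab, since entry on another test makes the second group possible. List both groups separately.
- Keep the all-ITT analysis as a sensitivity analysis.
- Apply the same restriction and listings to the Phase I analysis in SAP 15.
- Align the Protocol 6.9 rate (one negative) with the SAP (two negatives).

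First confirm in the full Table of Events that a baseline or Day 1 rRT-PCR mucosal swab is scheduled. The cost is a few sentences and a somewhat smaller denominator, which may also lose some infected subjects who lack a baseline rRT-PCR swab. Because the restriction uses a pre-treatment value, the randomized comparison is preserved.

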12.1.12.1.1. Nasopharyngeal and Oropharyngeal (optional) swabs

Using only synthetic fiber swabs with plastic shafts. Nasopharyngeal swab: Insert a swab into the nostril parallel to the palate. Leave the swab in place for a few seconds to absorb secretions. Swab both nasopharyngeal areas with the same swab. Optional Oropharyngeal swab: Swab the posterior pharynx, avoiding the tongue.

Do not use calcium alginate swabs or swabs with wooden shafts, as they may contain substances that inactivate some viruses and inhibit PCR testing. Place swabs immediately into sterile tubes containing 2-3 ml of viral transport media. Nasopharyngeal and oropharyngeal specimens should be kept in separate vials and labeled accurately.

12.1.12.1.2. Optional Sputum

The subject should rinse the mouth with water and then expectorate a deep cough sputum directly into a sterile, leak-proof, screw-cap sputum collection cup or sterile dry container. Samples should be labeled accurately.

12.1.12.1.3. Serum

Collect 1 tube (5-10 mL) of whole blood in a serum separator tube. Serum separator tubes should be stored upright for at least 30 minutes, and then centrifuged at 1000-1300 relative centrifugal force (RCF) for 10 minutes before removing the serum and placing it in a separate sterile tube for testing. Samples should be labeled accurately. Serum is not required to be collected during the Follow Up Period if the prior sample tested negative.

12.1.12.1.4. Endotracheal Aspirate

Endotracheal aspirate should be collected for intubated subjects only as outlined in Table of Events, [Section 7, Table 3](#). Sample should be collected per institutional practice. Samples should be labeled accurately.

12.1.12.2. Hematology

Hematology panel including complete blood count (CBC) with differential, including red blood cell (RBC) count, hemoglobin, hematocrit, white blood cell (WBC) count (with differential), platelet count, and mean platelet volume (MPV) will be collected as outlined in Table of Events, [Section 7, Table 3](#).

12.1.12.3. Blood Chemistry

Chemistry panel including sodium, potassium, calcium, carbon dioxide (bicarbonate) CO₂, chloride, blood urea nitrogen (BUN), creatinine, lactate dehydrogenase (LDH), glucose, albumin, total protein, alkaline phosphatase, bilirubin (total and direct), aspartate aminotransferase/serum glutamic oxaloacetic transaminase (AST/SGOT), alanine aminotransferase/serum glutamic pyruvic transaminase will be collected as outlined in Table of Events, [Section 7, Table 3](#).

Estimated Glomerular Filtration Rate (eGFR) will be calculated as part of the treatment eligibility assessment.

12.1.12.4. Coagulation

Coagulation tests including, prothrombin time (PT), partial thromboplastin time (PTT), International normalized ratio (INR) or activated partial thromboplastin time (aPTT), and fibrinogen will be measured locally at Treatment Eligibility Period and prior to first CYNK-001 infusion by local lab, then as clinically indicated, as outlined in the Table of Events, [Section 7, Table 3](#).

